4.6 Randomisation and allocation

Participants are allocated to one of the three trial arms using a centralised computerised randomisation system created by CHaRT.

Random allocation uses the minimisation covariates: Region; gender; age (< 45year, 45-64 years and \geq 65 years); residential status (care home vs community); previous blockages requiring intervention in last 6 months (0 vs \geq 1); previous S-CAUTI requiring antibiotics in last 6 months (0 vs \geq 1); Urine pH (normal vs acidic vs alkaline).

Participants will be randomised 1:1:1 to one of the following:

- Intervention arm (A): Saline washouts. A policy of weekly prophylactic normal saline (NaCl 0.9%) catheter washouts plus standard LTC care.
- Intervention arm (B): Acidic washouts. A policy of weekly prophylactic acidic (Citric acid) catheter washouts plus standard LTC care.
- Control arm (C): Standard LTC care only (i.e. no prophylactic catheter washouts)

Where deemed clinically necessary by the doctor / nurse in charge, the pragmatic design of the study permits the following changes to the washout policies:

• An increase in the frequency of the LTC washouts, at the onset of the study or following regular review during the course of the study

• A change in the type of washout, at the onset of the study or following regular review during the course of the study

• The use of prophylactic washouts in the control arm, following regular review during the course of the study (but not at the onset of the study)

These changes will be implemented and any reasons for the change recorded in the medical notes and study records. The participant will remain in the study and be followed up as per protocol.

Participants are randomised only after eligibility is confirmed and following consent.

The Principal Investigator (PI) at site, or member of the local research team (with delegated authority), accesses the web based system. Minimisation characteristics are entered into the web-based system, which returns the allocation status. Participants are informed of their allocated pathway following randomisation. If the participants are not present at the time of randomisation,

they are contacted by the research team to inform them of the allocated pathway after randomisation.

4.7 Delivery of the intervention

There are no restrictions on the type or route of LTC used. All participants receive their written standard LTC care plan from their local health team as per standard care – this may differ according to region/ country e.g. Catheter Passports are used in Scotland. If a participant does not have a written standard LTC care plan, the research team inform the local healthcare team and recommend that such plan should be in place as soon as practical. The research team also sign post the local healthcare team to the current guidelines from the government, national bodies and NICE³. Its best practice for the standard LTC care plan to include advice on: adequate hydration, securing the catheter position, avoidance of catheter kinking, how often the catheter and the catheter bag/valve need to be changed, advice on how to prevent and manage complications and the contact details of the participant's healthcare team (nurse in charge) in case they need to contact for catheter related complications.

All participants continue their ongoing regular review by their local healthcare team as per standard NHS care.

Study arms A (Saline washouts) and B (Acidic washouts):

In addition to standard LTC care described above, participants/ designated persons are asked to use catheter washout on weekly basis using 100 mls of normal saline (NaCL 0.9%) solution (study arm A) or 2 x 30ml of acidic solution (citric acid 3%; study arm B). Participants and/or their relative, friend or other informal carer are provided with a leaflet explaining the best practice technique in performing LTC washouts with special attention to minimise the breakage of the closed drainage system integrity.

Participants and/or their relative, friend or other informal carer receive additional training to enable them to self-administer the LTC washout. Training is delivered by their DN or an appropriately trained member of the local study team (1-2 hours) at the participant's home, GP practice, other appropriate setting (whichever is most suitable). This may be repeated to ensure mastery of the best practice technique described below. LTC washout is a simple procedure undertaken at the same time as the LTC bag/ valve change. Previous research has shown that this technique is rarely a barrier to participation ^{15, 16}. Our survey of community and urology nurses indicated that the technique can be mastered after 1-3 hours of training for the majority of participants. Participants or relatives, friends or other informal carers having difficulties with the washout technique can be offered more training. The need for more is monitored in the pilot study.

If a health professional (nurse or health care assistant) usually changes the LTC bag/ valve for a specific participant (for special medical or social indications especially those in care homes) then they will be asked to undertake the above training and perform the washouts within the study.

Participants will receive the catheter washouts free of charge on regular intervals (up to 6 deliveries over 24 months) through a courier or Royal Mail.

4.8 Administration arrangements post-recruitment

Following trial entry, the trial office:

- Informs the participant's GP of the randomised allocation (by letter enclosing information about CATHETER II and Study Office contact details) if the participant consents for this
- Informs the participant and relative, friend or informal carer (if applicable) of the randomised allocation

The local research team:

• Give a copy of the consent form to the participant and relative, friend or informal carer (if applicable)

- File a copy of the consent form/s in the relevant medical notes (primary care or secondary care or care home, depending where the patient is recruited) along with information about the trial
- Enter trial data regarding the participant into the bespoke trial website
- Maintain trial documentation at site
- Return a copy of the signed consent form/s to the Trial Office in Aberdeen.

5. OUTCOME MEASURES

5.1 Primary outcome measure

The primary clinical outcome is catheter blockage requiring intervention up to 24 months post randomisation expressed as number per 1000 catheter days.

- Intervention is defined as any of the following: unplanned catheter removal or change or washout performed by the participant/ designated person or required unplanned visits to/from any healthcare provider, or hospital admission.

The primary economic outcome is the incremental cost per quality adjusted life year (QALY) gained for each washout policy compared to standard LTC care only.

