4.4.1 Potential participants

Potential participants are given ample time to read and understand the fully comprehensive CATHETER II PIL. A pictorial and simple text information are also available to help explain the study. All potential participants are given opportunity to ask questions and have these answered before giving their informed decision on whether to join the study and sign the study consent form.

Signed consent forms are obtained in all centres by an appropriately trained member of the local research team who is listed on the delegation log. The participant's permission is sought to inform

their GP that they are taking part in this trial. Potential participants are also informed in the patient information leaflet that their contact details will be used to send them the washout solutions (if they are randomised to one of these arms), and that contact details will be shared with the courier company or Royal Mail who will deliver the washout solutions.

Consent forms that are returned by post are checked, signed and dated with the date of receipt. No study specific activities take place before consent is given.

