6.3 Follow-up

Participants (or the relative, friend or informal carer carrying out the washout) record LTC related events on their LTC calendar/diary including: LTC blockage requiring intervention (as defined in section 5.1); LTC change and the reason; adverse events such as S-CAUTI; antibiotics use for S-CAUTI; emergency catheter washout and its indication; treatments in primary or secondary care. The CATHETER II LTC diary is adapted from a purpose built diary that has been successfully used in an RCT in this field (permission already obtained from Wilde et al 2017¹)

The primary outcome, a number of the secondary outcomes, adverse events, and adherence are collected approximately monthly for 24 months from the participant and/or the relative, friend or informal carer carrying out the washout. A member of the research team, as delegated, completes the CRF over the phone or by agreed methods e.g. post/ email. A face to face interview will be arranged by the research team if/ when appropriate e.g. significant missing data from the monthly

contact. Where local site teams capture follow up information directly to the CATHETER II electronic CRF, the electronic record is the source data.

The EQ-5D-5L, the ICIQ-LTCqol, GSE Scale and the ICECAP-A/ or ICECAP-O and satisfaction with treatment are completed by participants with or without assistance from their relative, friend or informal carer at 6, 12, 18, and 24 months after randomisation.

Participants and their relative, friend or informal carer, if applicable, are asked to complete a time and travel questionnaire at 18 months after randomisation. This is to be used to estimate costs to participants.

We offer and use all methods of delivery and collection of questionnaires and reminders including use of research teams, telephone, post, e-mail (e-mail verification is used to validate e-mail addresses), and web based taking into account each participant and/or their relative, friend or informal carer(if applicable) stated preferred means of receiving and completing the measures (recorded on the contact preference form). One reminder for the questionnaire is sent to participants and their relative, friend or informal carer, if applicable, by post, email, or phone taking into account any preferences they may have for mode of communication.

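### One route to a primary event, a home washout for a blockage, is trained and supplied only in arms A and B, so a sensitivity analysis on route is needed

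*Protocol*

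**What the plan says.** The primary outcome is set in section 5.1: "The primary clinical outcome is catheter blockage requiring intervention up to 24 months post randomisation expressed as number per 1000 catheter days". The same section says what makes a blockage count. The list includes "unplanned catheter removal or change or washout performed by the participant/ designated person or required unplanned visits", and ends with hospital admission. Read with the word unplanned carried through the list, an unplanned washout by the participant or a helper is enough by itself, with no contact with a healthcare provider.

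The means to do this come with allocation. Section 4.7, in the part headed for arms A and B, says that participants or carers "receive additional training to enable them to self-administer the LTC washout" and, under the same heading, "Participants will receive the catheter washouts free of charge on regular intervals". Section 4.4.1 makes the condition explicit: contact details are used to "send them the washout solutions (if they are randomised to one of these arms". Arm C has standard care only (section 3.1).

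The trial is open (section 3). Section 6.3 takes events from a diary kept by the participant or carer, followed by roughly monthly contact. That diary also records "emergency catheter washout and its indication", with no restriction by arm. The protocol gives no physical criterion separating partial from complete blockage and describes no blinded adjudication.

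**The concern.** Take a catheter that is draining slowly. In arm A or B, someone trained, with solution in the house, can flush it at once, and the episode becomes a primary event. In control the same episode counts if it goes on to a catheter change, an unplanned visit or an admission. If it settles first, it is not counted. A complete blockage should reach the count in every arm by one route or another, so any difference lies in partial or early episodes.

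If this happens to any extent, the washout arms collect extra events for a reason unrelated to how often catheters block. The rate ratio moves toward or past 1. A real benefit could be missed, or an inert washout could look harmful. An analysis under the single definition could not reveal this.

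**Working it through.** **Inputs (section 8.1).** Rates 11.8 and 8.9 per 1000 days; dispersion k = 0.6; 200 per arm; follow-up 730 − 50 = 680 days; 90% power; significance level 2.5%, sidedness not stated.

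**Formula.** Negative binomial comparison of two rates. V = (1/680)(1/r0 + 1/r1) + 2k, SE = √(V/200), n per arm = (z_α + z_β)² V / (ln RR)², power = Φ(|ln RR|/SE − z_α).

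**The plan's own figure.** RR = 8.9/11.8 = 0.754 and ln RR = −0.282. Expected events per person are 0.0118 × 680 = 8.02 and 0.0089 × 680 = 6.05. V = 1/8.02 + 1/6.05 + 1.2 = 1.490, SE = 0.0863.
- One-sided 2.5%: n = (1.960 + 1.282)² × 1.490/0.282² = 197; power at 200 is 90.5%. This reproduces the protocol.
- Two-sided 2.5%: n = (2.241 + 1.282)² × 1.490/0.282² = 232; power at 200 is 84.8%. This does not.

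Both readings are carried below, each with its own starting power.

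**Extra events in a washout arm.** Let f be the net proportional excess of events counted in a washout arm, relative to control, only because home washout is at hand there. The documents give no value for f, so a range is assumed. The observed RR is 0.754 × (1 + f).

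| f | Extra events per person (6.05 × f) | Observed RR | Power, one-sided 2.5% | Power, two-sided 2.5% |
|---|---|---|---|---|
| 0 | 0 | 0.754 | 90.5% | 85% |
| 5% | 0.30 | 0.792 | 77% | 68% |
| 10% | 0.61 | 0.830 | 59% | 47% |
| 20% | 1.21 | 0.905 | 21% | 14% |

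The target effect disappears at f = 11.8/8.9 − 1 = 32.6%, about 2.0 extra events per person over 680 days.

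If washouts do nothing, the observed RR is 1 + f. At two-sided 2.5%, the chance of a significant result against washouts is 13% at f = 10% and 47% at f = 20%.

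**The opposite error.** Suppose washouts do nothing and home-washout events are left out, so that a share d of true blockages in a washout arm is cleared at home and lost, while the same blockages in control lead to a visit and count. The observed RR is 1 − d. At two-sided 2.5%:
- d = 10%: RR 0.90, V = 1.463, SE = 0.0855, chance of false benefit 16%.
- d = 20%: RR 0.80, V = 1.480, SE = 0.0860, chance of false benefit 64%.

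The share d is assumed, as f is.

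**Loss of precision under the narrower count.** If 20% of events were lost equally in both arms, V rises from 1.490 to 1.2 + (0.290/0.8) = 1.562. Power goes from 90.5% to 89.1% one-sided, or from 84.8% to 82.9% two-sided. The dispersion term 2k = 1.2 dominates the variance, so fewer events cost little.

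**The case against.** The strongest reply is that counting home-cleared blockages is a safeguard. Without it, washout participants could clear at home blockages that would bring a control participant to a nurse, and the washouts would look better than they are. This stands, and it is why section 5.1 should not be replaced.

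Secondly, there is one definition for all arms, and the event must be a blockage. Scheduled weekly washouts are not events. A reader might infer that the definition itself depends on allocation. The text does not support that: what differs is opportunity.

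Thirdly, a reader might infer that control has no such route and that nothing offsets the difference. The protocol contradicts this. Every participant must be able to do washouts or have a designated person who can (section 4.2). Washouts are already in use for managing blockage (section 1.1). Control may start prophylactic washouts after review (section 4.6). A control participant's unplanned visit for a blockage counts. These points reduce the gap but do not close it, since trial training and supply still follow allocation.

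Fourthly, no passage says that partial blockages settle unaided in control. The mechanism is plausible but not documented, and its size is unknown.

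Lastly, the SAP was not available and may already contain a suitable sensitivity analysis. Hospital admissions and GP or nurse visits for catheter complications are also secondary outcomes (section 5.2), which gives a partial check.

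**Conclusion.** The concern holds in a limited form. The unequal provision for one qualifying route is on the face of the protocol. Open allocation and diary reporting leave room for it to affect the count. The likely direction under the current definition is against washouts.

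The size is not known. The figures above illustrate a range and predict nothing: they assume a net excess of 5 to 20% in a washout arm, 680 days of follow-up and k = 0.6. On either reading of the 2.5% level a modest excess matters. At 10%, about 0.6 events per person, power falls from 90.5% to 59% one-sided or from 85% to 47% two-sided.

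A reader might go further and conclude that the primary definition should exclude home washouts. The documents do not support that, because the narrower definition carries a bias of similar consequence in favour of washouts. Neither definition is neutral. Together they show whether the conclusion depends on how home-cleared blockages are counted.

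**What to change.** Keep the section 5.1 definition as primary. Then:

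1. In section 6.3 and the CRF, record for every blockage in every arm how it was cleared: home washout only, catheter removal or change, unplanned healthcare contact, or admission.
2. In section 9, or in the SAP if it is not already there, pre-specify a key sensitivity analysis. Use the same negative binomial model, counting only blockages that led to unplanned catheter removal or change, an unplanned healthcare contact or admission.
3. Report by arm the number and rate of blockages managed solely by home washout.
4. State beforehand that the two analyses err in opposite directions, and that a conclusion of benefit or harm seen under only one of them will be described as not robust.

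The cost is small. The diary already captures emergency washouts and their indication, so the additions are a route field, one more model and one table. The drawback is that the conclusion may be less definite if the two analyses differ.

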5.2 Secondary outcome measures

Secondary outcomes include:

- S-CAUTI requiring antibiotics use (as defined by Pickard et al¹⁶)
- Duration of LTC in use, catheter change due to other reasons than blockage
- Adverse events
- Hospital admissions, GP/ nurse outpatient visits for catheter related complications
- Generic quality of life as assessed by EQ-5D-5L¹⁷ (EuroQol questionnaire 5 dimensions 5 levels)
- Condition specific quality of life assessed by ICIQ-LTCqol¹⁸ (International Consultation on Incontinence Modular Questionnaire – Long Term Catheter quality of life)
- Adherence to allocated interventions
- Patients' convenience and satisfaction assessed by an adapted version of the abbreviated Treatment Satisfaction Questionnaire for medication¹⁹
- Impact on day to day activities using The General Self-Efficacy Scale (GSE)²⁰ and ICECAP-A (ICEpop CAPability measure for Adults) (≤ 65 years) or ICECAP-O²¹ (ICEpop CAPability measure for Older people) > 65 years
- Time and travel costs for patients and their relatives, friends or informal carers
- Discontinuation of catheter use
- Events changing type and/or frequency (or cessation) of catheter washouts in arms B and C and rates of commencing on prophylactic washouts in arm A.

Qualitative study outcomes:

- Participants' experience of LTC-related AEs such as blockage, S-CAUTI, urinary incontinence, bladder pain
- Participants' attitudes/ preferences to washout versus no washout policies and expected outcomes (prior to randomisation or knowing their allocated study group) (acceptability);
- Participants' experience with washout/ no washout policies and evaluation of outcomes (satisfaction)
- Clinicians attitudes towards influence of washout policies on outcomes
- Participants' and clinicians' experience of training provided and enactment of the treatment skill. This would clarify the fidelity of the intervention.

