3.1 Interventions

The interventions being compared are:

- Intervention arm (A): Saline washouts. A policy of weekly prophylactic normal saline (NaCl 0.9%) catheter washouts plus standard LTC care.
- Intervention arm (B): Acidic washouts. A policy of weekly prophylactic acidic (citric) catheter washouts plus standard LTC care.
- Control arm (C): Standard LTC care only (i.e. no prophylactic catheter washouts)

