8.4 Internal pilot study

The internal pilot study (with stop/go criteria) is designed to establish whether the projected recruitment rate is achievable. We aim to set up the first 3 sites in calendar month 6, and then over the following 5 months open a further 28 sites, with a total of 31 site by the end of study month 11. By this time we aim to have recruited 100 participants. Considering the number randomised per month from each site as following independent Poisson distributions with mean and variance 0.9; then we can say:

ISRCTNxxxxx IRAS 259559

- 1) If we recruit at least 80 within the 111 centre months; we are within 2 standard deviations (SD) of the expected 100 and recruitment can continue without modification;
- 2) If we recruit between 60 and 80; we are between 4 and 2 SD of the expected 100. We would need to modify the recruitment approach for example, recruiting more centres, or allowing for more recruitment time at a centre, (setting up centres more quickly and/ or adding some extra months to lengthen the recruitment at the best recruiting centres). We would continue to monitor recruitment carefully to ensure that these recovery manoeuvres had worked.
- 3) If we recruit less than 60 we would be >4 SD from our target and we would enter discussions with the funder to determine whether the RCT is feasible.

During the pilot phase we are measuring the adherence to the intervention policies. That is the frequency of prophylactic washout in arms A and B. We would expect at least 80% of participants to be undertaking 60% of their washouts. If this threshold is not met, to improve it we may consider adapting or offering more training sessions.

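### Section 5.2 attaches the wrong arm letters to the secondary outcome on washout changes, so read literally it omits saline-arm changes and control-arm starts

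*Protocol*

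**What the plan says.** Section 3.1 defines the arms. Arm A is "Intervention arm (A): Saline washouts. A policy of weekly prophylactic normal saline (NaCl 0.9%) catheter washouts plus standard LTC care". Arm B is "Intervention arm (B): Acidic washouts. A policy of weekly prophylactic acidic (citric) catheter washouts plus standard LTC care". The third is "Control arm (C): Standard LTC care only (i.e. no prophylactic catheter washouts". The Protocol Summary and section 4.6 repeat these definitions with the same letters. Section 4.7 gives the washout instructions for A as saline and B as acidic. Section 8.4 describes pilot adherence as "the frequency of prophylactic washout in arms A and B".

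Section 4.6 allows three departures from the allocated policy where the clinician in charge considers them necessary. Washouts may be made more frequent, and their type may be switched; either can happen from the outset or after a later review. The third departure is worded as "The use of prophylactic washouts in the control arm, following regular review during the course of the study", with an explicit bar on doing so at the outset.

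The last item of the main secondary outcome list in section 5.2 is meant to report such events. It counts changes in type or frequency, or cessation, "of catheter washouts in arms B and C and rates of commencing on prophylactic washouts in arm A".

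**The concern.** The letters in this outcome do not match the arms. Commencing prophylactic washouts is a meaningful event in an arm that was not allocated them, which is C. Changing or stopping washouts is a meaningful event in the arms that were allocated them, which are A and B. Section 5.2 has it the other way round for A and C.

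Both hypotheses in section 2 compare a washout arm with standard care, and section 9 analyses them by intention to treat. Control participants who start washouts therefore stay in the control group, and saline participants who stop or switch stay in the saline group. How often each happens is what a reader needs in order to judge a small or null difference. If a report table, database query or registry entry were copied from section 5.2 as it stands, it would present the wrong events for two of the three arms.

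**Working it through.** The protocol gives no figure for this outcome, so there is nothing to reproduce. The check sets the sections side by side.

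| Arm | Allocation (Protocol Summary, 3.1, 4.6) | Departure allowed by 4.6 | Event counted by 5.2, read literally |
|---|---|---|---|
| A | Weekly saline washouts | Change of type, more frequent washouts | Starting prophylactic washouts |
| B | Weekly acidic washouts | Change of type, more frequent washouts | Change of type or frequency, stopping |
| C | No prophylactic washouts | Starting prophylactic washouts during the study | Change of type or frequency, stopping |

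1. *Which arms the first two departures concern.* Section 4.6 does not name the arms for changes of type or frequency, but it allows both from the outset. It bars washouts in the control arm at the outset. At that point the two changes can only refer to A and B.
2. *Which arm the third departure concerns.* Section 4.6 says the control arm, which is C in every definition.
3. *Comparison with 5.2.* The last two columns agree for B only. For A, changes and stopping are missing and an uninformative event takes their place, because every participant in A is allocated washouts. For C, starting is missing.
4. *Whether another labelling would make sense of 5.2.* It would be coherent if A were the control and B and C the washout arms. The Protocol Summary and sections 3.1, 4.6, 4.7 and 8.4 all contradict that labelling, and nothing else in the current text supports it.
5. *Size.* Section 8.1 plans 200 participants per arm. Two arms have the wrong event attached: 2 × 200 = 400 of 3 × 200 = 600. This counts participants to whom the wrong definition applies. It is not an estimate of how many events would be misreported, for which the protocol gives no figure.

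**The case against.** The best defence is that nothing need be lost. Section 4.6 requires changes, expressly including washouts in the control arm, to be implemented and recorded with reasons in the medical notes and study records, whatever the arm. Section 5.2 also lists adherence to the allocated intervention as a separate outcome, and section 6.3 collects adherence about monthly for 24 months. Most readers would see that starting prophylactic washouts can only be meant for the control arm. The statistical analysis plan, where tables are normally specified, is not at hand.

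Much of this stands, and it limits the consequence. It does not cure the wording. Section 8.4, where adherence is spelled out for the pilot, refers only to arms A and B, so the adherence outcome may or may not show control-arm starts. Table 1 has no row for washout changes, and the diary items in section 6.3 name emergency washouts but not the start of prophylactic ones. Recording an event is also not the same as naming it, by arm, as an outcome.

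A reader might infer several stronger things that the documents do not support:
- *That crossover would go unmeasured, or that the trial tables are wrong.* The recording rule and the adherence outcome count against the first. The second cannot be known from the protocol alone.
- *That the arm A figure would be close to complete by design.* The protocol gives no uptake figure. Its only benchmark, in section 8.4, is that at least 80% of participants do 60% of their washouts.
- *That arm C can have no changes or stopping at all.* A control participant who starts washouts under section 4.6 could later change or stop them. Arm C has no allocated washouts to change.
- *That the error costs power.* Crossover dilutes the contrast equally whether the outcome is labelled rightly or wrongly, the protocol states no crossover rate, and correcting the letters restores no power.

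**Conclusion.** The point holds as an internal inconsistency in one secondary outcome. The arm letters in section 5.2 contradict every definition of the arms in the current protocol, and no other section reconciles them. Taken literally, the definition is right for arm B and wrong for arms A and C. It omits saline-arm changes and stopping, and it omits the control-arm starts that section 4.6 permits.

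The conclusion rests on the current text alone and needs no numerical assumption. The primary outcome (5.1), allocation (4.6), sample size (8.1) and intention-to-treat analysis (9) do not depend on this item and are unaffected. The error should be corrected because a listed outcome ought not to need guessing and this one bears on how both primary comparisons are read. It does not threaten the validity of the trial.

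**What to change.** Reword the item in section 5.2 so that changes in washout type or frequency, and cessation, are counted in arms A and B, and the rate of starting prophylactic washouts is counted in arm C. Then check the case report form, the database and the report shells, including those for the Data Monitoring Committee, for the same swap. Align the statistical analysis plan if it repeats the letters.

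The cost is a one-line protocol correction and a short document check. No change is needed to the interventions, the permitted departures, the sample size or the primary analysis.
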